#### LIST OF ABBREVIATIONS AND RELEVANT DEFINITIONS

AE Adverse Event

AR Adverse Reaction

ASD Autism Spectrum Disorder

ASQ Attachment Style Questionnaire

ECR-R Experiences in Close Relationships Revised

**EU** European Union

**EudraCT** European drug regulatory affairs Clinical Trials

**HSL** Hechtingsstijllijst

METC Medical Research Ethics Committee (MREC); in Dutch: medisch-ethische

toetsingscommissie (METC)

**RDM** Research Data Management

RSQ Relationship Scales Questionnaire

(S)AE (Serious) Adverse Event

Sponsor The sponsor is the party that commissions the organisation or performance

of the research, for example a pharmaceutical

company, academic hospital, scientific organisation or investigator. A party

that provides funding for a study but does not commission it is not regarded as the sponsor, but referred to as a subsidising party.

SRS-A Social Responsiveness Scale – Adult version

SUSAR Suspected Unexpected Serious Adverse Reaction

**UMC** University Medical Center

WMO Medical Research Involving Human Subjects Act; in Dutch: Wet Medisch-

wetenschappelijk Onderzoek met Mensen

#### **SUMMARY**

**Rationale:** Previous research on autism spectrum disorder (ASD) and attachment has improved understanding of the aetiology and development of the disorder. Research on adults with ASD, however is scarce. In the current study, we focus on attachment in adults with ASD.

**Objective**: The aim of the current study is to explore attachment styles of adults with ASD and examining the relationship between attachment and ASD.

Study design: Cross-sectional design: data will be analysed at a specific point in time.

**Study population:** Adults (>18 years) with ASD, and without intellectual disability.

Participants will be recruited from SARR Autism Rotterdam and Antes, both part of Parnassia Group in the Netherlands. SARR Autism Rotterdam is specialized in psychodiagnostic assessments and interventions for children, adolescents, and adults with ASD. Antes and Parnassia Group are multisite mental health institutes specialized in psychodiagnostic assessments and interventions for adults with a broad range of psychiatric disorders, including ASD. The study requires 60 participants.

Intervention (if applicable): not applicable

**Main study parameters/endpoints:** Main study parameters are SRS-A score (ASD characteristics), ASQ (attachment style) and ECR-R (attachment anxiety and attachment avoidance).

Nature and extent of the burden and risks associated with participation, benefit and group relatedness: Participants are asked to complete three online questionnaires, each taking no more than 15 minutes to complete. The questionnaires collect participants' information on their ASD characteristics and their experiences of interpersonal relationships. We do not expect this to be burdensome, as they are already familiar with diagnostic assessment. For individuals with ASD, the principal psychological benefit of knowing their attachment style may be that in those with insecure attachment this knowledge may function as a means of treatment.

#### 1. INTRODUCTION AND RATIONALE

Autism spectrum disorder (ASD) is a neurodevelopmental disorder with early onset, and typical characteristics throughout one's lifetime. It is called a spectrum disorder because of variety in phenotypic presentation and severity of symptoms (Lai et al., 2013). Kanner (1943) described ASD as an inability to form effective contact with others. In the late 1970s, lack of attachment was mentioned as one of the characteristics of ASD (Rutter, 1978). DSM-III American Psychiatric Association, 1980) described ASD as a failure to develop normal attachment behaviour. However, recent research indicates that individuals with ADS are able to form secure attachment, albeit at lower rates and with more challenges (Chandler & Dissanayake, 2014; Giannotti & de Falco, 2021; Rutgers et al., 2004; Teague et al., 2017). In DSM-5-TR (American Psychiatric Association, 2022). Core features are persistent deficits in social communication, social interaction, and restricted, repetitive patterns of behaviour, interests, or activities. The social disability is multifaceted with deficits in social-emotional reciprocity, social non-verbal communication, and developing, understanding, and maintaining relationships. Both ASD and insecure attachment affect social functioning and relationships and little is known about attachment in adults with ASD and the relationship between ASD and attachment in adults.

For more than over 60 years, the concept of attachment is one of the most and well-known concepts in the field of clinical psychology. John Bowlby (1969; 1973; 1980), the first attachment theorist, formulated his attachment theory which has led to one of the major theories of affect regulation, interpersonal functioning, and psychopathology. Development of attachment begins in early infancy: children establish attachment bonds with their caregivers, serving as an evolutionary function keeping the child close to the caregiver in times of stress to increase chance of survival. During child development, attachment behaviours adapt. In infants, toddlers, and pre-schoolers, attachment behaviours are: crying, clinging to caregivers, wariness of strangers, preference for a specific caregiver, and using the caregiver as a safe-base to return when exploring the environment (Bowlby, 1969). In middle childhood (between 6 and 12 years of age), attachment behaviours become less dependent on the their physical proximity to caregivers. Instead, caregivers' unconditional availability and responsiveness, influence attachment behaviours (Kobak et al., 2005).

Ainsworth and colleagues (1978) extended Bowlby's attachment theory by delineating individual differences in attachment patterns through observation of behaviour of infants of 12 to 24 months approximately in response to separation from and reunion with the caregiver (i.e., the well-known Strange Situation procedure (Ainsworth et al., 1978). Three different patterns of interaction and behaviour shown by infants towards their caregiver were discovered: secure, anxious, and avoidant. Securely attached children were distressed

during separation, but recovered quickly, showing joy, affection, easily soothed upon reunion, and more openness and flexibility towards exploring the environment. Anxious attached children were highly distressed during separations, showing anger and resistance upon reunion, yearning for physical contact and comfort with contradictory and ambivalent responses towards the mother, highly sensitive to potential unavailability, maximizing their efforts to remain in close contact with the caregiver. Avoidant attached children showed little distress when separated, avoiding proximity upon return, suppressing their needs and feelings of distress and giving up their proximity-seeking efforts (Ainsworth & Bell, 1970). A fourth attachment style was added, which is called the disorganized attachment style (Main & Solomon, 1986). Children with this style show chaotic, contradictory behavior (indifferences upon mother's return after excessive distress during separation), misdirected (seeking proximity to a stranger instead of a parent after separation) or stereotypical behavior (pulling hair with dazed expression, even though the parent is available), stilling and freezing (unable to choose between proximity or avoiding the parent, stops moving as in trance, dissociated from regular thought processes) for a substantial amount of time, or they even fear the parent in stressful circumstances. Their behaviour is bizarre and incoherent, indicating stress and anxiety the child cannot resolve because the parent is source of fright as well as the only potential haven of safety (Main & Solomon, 1986; Van IJzendoorn et al., 1999).

Bowlby (1980) argued that attachment processes continue to influence close relationships across the life span. In adulthood, internal working models of attachment are generally conceptualized as sets of global beliefs about self and others, resulting in a combination of four attachment styles (secure, preoccupied, dismissing and fearful) (Bartholomew & Horowitz, 1991; Griffin & Bartholomew, 1994). Individuals with a secure attachment style have positive views of self and others, and are at ease in becoming emotionally close and depending to others. Preoccupied attached individuals have a positive view on others, but a negative view on self, desiring extreme intimacy with others who do not meet their attachment needs. Avoidant – dismissing individuals have a positive self-model and a negative other-model, feeling comfortable without close emotional relationships.

Intimacy is avoided because independence, self-reliance and maintaining autonomy is very important for them. The Avoidant – Fearful individuals have a negative view on both self and others, avoiding intimacy for the fear to be hurt.

Until now, studies examining attachment in ASD mainly focused on children (Bauminger et al., 2010; Capps et al., 1994; Davidson et al., 2022; Davidson et al., 2015; Dissanayake & Sigman, 2001; McKenzie & Dallos, 2017; Minnis et al., 2020; Rutgers et al., 2004; Sivaratnam et al., 2018; Teague et al., 2017; Van IJzendoorn et al., 2007; Willemsen-

Swinkels et al., 2000). A review study on ASD and attachment showed 40%-63% children with ASD are securely attached to their caregiver, comparable to children without ASD.

Secure attachments appear to act as a protective factor in the social and cognitive development of children with ASD (Teague, 2017). When demonstrating secure attachment, children with ASD show more complex play behaviours (Naber et al., 2008), more joint attention (Naber et al., 2007), improved social skills and educational opportunities and outcomes (Bauminger et al., 2010. These findings are consistent with observations from the typically developing literature and with predictions from attachment theory (Teague, 2017). The severity of ASD and developmental delay are both associated with less secure attachments (Naber et al., 2006), but there is a lack of consensus on the extent to which attachment insecurity is a function of either developmental delay or the severity of autism symptoms. To the best of our knowledge, research on attachment in adults with ASD is scarce. To date, only one study on attachment in adults with high functioning ASD (*N*=20) found a minority (15%) to be securely attached comparable with a general clinical sample and lower than non-clinical samples, and attachment security was found not to be related to ASD characteristic and IQ (Taylor et al., 2008).

Very little research has investigated the relationship between attachment and behaviour and emotional problems in children with ASD (Teague et al., 2017). The aim of this study is to explore attachment styles in adults with ASD and examining the relationship between attachment and ASD. For individuals with ASD, the principal psychological benefit of knowing their attachment style may be that in those with insecure attachment this knowledge may function as a means of treatment.

#### 2. OBJECTIVES

Primary Objective: Exploring the relationship between ASD and attachment by describing how attachment styles are distributed in an adult population with ASD. We calculate correlations between ASD characteristics based on the SRS-A and attachment styles, attachment anxiety and attachment avoidance, as well as between attachment and level of education and having a relationship.

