#### 4.2 Inclusion criteria

Inclusion criteria are: a DSM-5 ASD diagnosis, age 18-65 years and no intellectual disability (IQ >80).

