#### 8. METHODS

# 8.1 Study parameters/endpoints

# 8.1.1 Main study parameter/endpoint

Main study parameters are the SRS-A score, the ASQ and ECR-R.

The *Social Responsiveness Scale – Adult version* (SRS-A) (Constantino, 2005; Dutch translation: Noens et al., 2012), a screening tool for identifying possible ASD characteristics in adults suspicious for ASD, is 64-item self-report questionnaire measuring various dimensions of interpersonal behavior, communication, and rigid, repetitive behaviour and interests, characteristic for adults with ASD. Each item is rated on a 1-4 point scale. The SRS-A showed average to good internal consistency and test-retest reliability, adequate content validity, and good congruent validity (Noens et al., 2012). The Cronbach's alpha for the SRS-A scales were for Social awareness .80, Social communication .82, Social motivation .81, and Restricted interests & repetitive behavior .81 (Bezemer et al., 2020).

The Attachment Styles Questionnaire (ASQ; Mosterman & Hofstra, 2015), translation of the Dutch Hechtingsstijllijst (HSL) (Oudenhoven et al., 2003), is a questionnaire consisting of 24 items based on four vignettes (Bartholomew & Horowitz, 1991) and the Relationship Scales Questionnaire (RSQ; Griffin & Bartholomew, 1994). The ASQ assesses four attachment styles (secure, preoccupied, fearful, and dismissing). The 5-point rating scale ranges from 1 (*strongly disagree*) to 5 (*strongly agree*). The internal consistencies (Cronbach's alpha) were 0.75 for the secure style, 0.80 for the preoccupied style, 0.79 for the fearful style, and 0.62 for the dismissing style (Mosterman & Hofstra, 2015).

The Experiences in Close Relationships Questionnaire Revised (ECR-R) (Fraley, Waller, & Brennan, 2000; Dutch translation by Conradi et al., 2006) measures adult attachment within romantic relationships in past and present in 36 items, consisting of two subscales of 18 items each (attachment anxiety and attachment avoidance). Each item is rated from 'strongly disagree' (1) to 'strongly agree' (7). The ECR-R is currently the most commonly used and recommended self-report measures with good psychometric properties (Conradi et al., 2006; Sibley et al., 2005; Sibley & Liu, 2004). Cronbach's alpha was 0.88 for attachment avoidance and 0.86 for attachment anxiety. In a validation study of the Dutch version, factor structure could be replicated, reliability was stable over time and there was good evidence for its construct validity

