#### 10. STATISTICAL ANALYSIS

# 10.1 Primary study parameter(s)

Statistical analyses were performed using Statistical Package for the Social Sciences version 27 (SPSS Version 27, IBM, New York, NY, USA). First descriptive statistics were used to analyze participants' demographic data.

Spearman correlation coefficients were used to calculate the correlations between SRS-A scores and ASQ scores, and between SRS-A scores and ECR-R scores.

Multiple regression was used to test whether level of education and having a relationship influence a SRS-A score and attachment and whether this is a positive or a negative effect. For the analyses p-value of < .05 was considered statistically significant.

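### Does the descriptive part of the primary objective lack an analysis because section 10.1 names no summary of the ASQ?

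*Combined protocol and SAP*

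**What the plan says.** Section 2 gives one primary objective: to explore the relationship between autism spectrum disorder (ASD) and attachment by "describing how attachment styles are distributed in an adult population with ASD". A second sentence adds correlations of the SRS-A with attachment styles, anxiety and avoidance, and of attachment with education and relationship status.

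Section 8.1.1 describes the ASQ as 24 items rated 1 to 5, covering four styles (secure, preoccupied, fearful, dismissing), with a reliability figure for each. It gives no rule for assigning a participant to a single style.

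Section 10.1 opens with "First descriptive statistics were used to analyze" and names demographic data as their subject. It continues: "Spearman correlation coefficients were used to calculate the correlations between SRS-A scores and ASQ scores", with the same for the ECR-R, and then a multiple regression. Sections 10.2 and 10.3 both say that there is nothing further.

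The only figures on how attachment is distributed are in section 1. A review of children reports that "40%-63% children with ASD are securely attached to their caregiver, comparable to children without ASD", and a study of 20 adults "found a minority (15%) to be securely attached comparable with a general clinical sample and lower than non-clinical samples".

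**The concern.** Part of the primary objective is descriptive, and the analysis section assigns nothing to it. Read literally, section 10.1 yields a demographic table, correlations and a regression, but no account of the attachment styles themselves.

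The form of the summary also looks open. Section 10.1 works with ASQ scores. Section 1 speaks of style as something a person has ("the principal psychological benefit of knowing their attachment style may be that in those with insecure attachment") and cites percentages securely attached. Every participant has ASD (section 4.2: "Inclusion criteria are: a DSM-5 ASD diagnosis, age 18-65 years"), and there is no comparison group. A reader may therefore expect the cited percentages to serve as the yardstick, and score summaries cannot be set against percentages. If categories were used, the classification and tie rule could shift the reported percentages, and a rule chosen after seeing the data would leave room for selective reporting.

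**Working it through.** **1. Is the summary assigned anywhere?** The relevant sections, side by side:

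| Section | What it contributes |
|---|---|
| 2 | descriptive aim, then correlations |
| 8.1.1 | ASQ items, rating scale, reliability; no summary, no classification rule |
| 10.1 | descriptives for demographics; ASQ scores in correlations; attachment in a regression |
| 10.2, 10.3 | none |

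No sentence assigns a summary to the ASQ. Equally, none rules one out: section 10.1 says what the first descriptive step covered and does not confine descriptive statistics to it.

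**2. Is a comparison with the background percentages planned?** Sections 2, 3, 8.1.1 and 10.1 mention no external reference value. The 15% and 40%-63% figures appear only in section 1. The latter concerns children's attachment to a caregiver, whereas the ASQ is a self-report of adult style. The documents do not show that these are comparable.

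**3. Does the choice of form put the description at risk at n = 60?** The plan gives no figure of its own to reproduce here; the calculation in section 4.4 concerns the correlations. The inputs are n = 60 (section 4.1), 15% of N = 20, i.e. 3/20 (section 1), and the assumption that all 60 complete the ASQ.

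*Scores.* The 95% half-width of a mean is t(0.975; 59)/√60 = 2.001/7.746 = 0.258 SD.

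*Percentages.* The Wilson interval is [p + z²/2n ± z√(p(1−p)/n + z²/4n²)] / (1 + z²/n), with z = 1.96.

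- 9/60 (15%): centre (0.150 + 0.0320)/1.0640 = 0.1711; half-width 1.96 × √(0.002125 + 0.000267)/1.0640 = 0.0901; interval 8.1% to 26.1%.
- 24/60 (40%): centre (0.400 + 0.0320)/1.0640 = 0.4060; half-width 1.96 × √(0.004000 + 0.000267)/1.0640 = 0.1203; interval 28.6% to 52.6%.
- 38/60 (63%): by the same formula, 50.7% to 74.4%.

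Both forms describe the sample with ordinary precision. That precision comes from the 60 participants, not from a sentence in section 10.1.

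**4. How firm would the adult yardstick be?** The same formula for 3/20 gives a centre of (0.150 + 0.0960)/1.1921 = 0.2064 and a half-width of 1.96 × √(0.006375 + 0.002401)/1.1921 = 0.1540, so 5.2% to 36.0%. By Fisher's exact test against 3/20, a count out of 60 differs at the 0.05 level at the low end for 0 (p = 0.014) or 1 (p = 0.046). At the high end it differs only from 25 upwards (24/60: p = 0.056; 25/60: p = 0.034). A formal comparison with the adult figure would say little across most of the plausible range, so its absence from the plan costs little.

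**The case for a change.** The strongest case for a change is that the description is part of the only objective, that one or two sentences would settle it, and that the wording supports two different outputs. In percentage form, 60 participants could be informative: 9/60 excludes 40% and 24/60 excludes 15%. Against a fixed 15%, an exact two-sided binomial test would have 84% power at a true 30% (55% at a true 25%). In score form, the documents give no reference mean to read the result against. A classification rule chosen late could also move the percentages.

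Some of this stands. The sentence is missing, the wording of section 2 leaves both forms open, and a classification and tie rule would need to be reported if categories were used.

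The rest does not carry over to this plan. The power and exclusion figures are arithmetically right, but they belong to a comparison the authors do not propose. They also treat the background percentages as comparable with an ASQ classification, which the documents do not show. A description needs no benchmark. The documents give no ASQ reference means, but section 8.1.1 cites a validation study for the instrument; its content cannot be seen here, so it cannot be concluded that the authors lack reference values or a scoring rule. The risk of selective reporting is limited because no hypothesis test hangs on the description, and section 10.1 already requires the four scores, so their summary can be shown alongside any categories.

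**Conclusion.** The gap exists, but it is one of detail. Section 10.1 omits a routine line that any analyst would supply before correlating the ASQ scores, and either customary form would meet the descriptive aim: mean and SD (or median and IQR) per style, or counts and percentages per style. No stated rule is wrong, and the correlations, the regression and the sample size are untouched.

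The size is correspondingly small: no effect on any test result, and ordinary precision in either form (about 0.26 SD for a mean; 8% to 26% around 9/60). This rests on three things: that all 60 complete the ASQ, that the report includes the usual descriptive table of the questionnaires, and that no comparison with the 15% or 40%-63% figures is intended, as none is written. If the authors later decided to test against those figures, the classification rule and the comparability of the instruments would become real questions. They are not questions for the plan as it stands.

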#### 3. STUDY DESIGN

A cross sectional design will be used (outcomes on SRS-A, ASQ, and ECR-R).

#### 4. STUDY POPULATION

# 4.1 Population (base)

Adults (>18 years) with ASD, and without intellectual disability. Participants will be recruited from SARR Autism Rotterdam and Antes, both part of Parnassia Group in the Netherlands. SARR Autism Rotterdam is specialized in psychodiagnostic assessments and interventions for children, adolescents, and adults with ASD. Antes and Parnassia Group are multisite mental health institutes specialized in psychodiagnostic assessments and interventions for adults with a broad range of psychiatric disorders, including ASD. The study requires 60 participants.

#### 4.2 Inclusion criteria

Inclusion criteria are: a DSM-5 ASD diagnosis, age 18-65 years and no intellectual disability (IQ >80).

#### 4.3 Exclusion criteria

Exclusion criteria are: acute psychosis, acute suicidality, psychotic disorder, intellectual disability (IQ < 80)

# 4.4 Sample size calculation

A priori power analysis was conducted using G\*Power version 3.1.9.7 (Faul et al., 2007) to determine the minimum sample size required to test the relationship between ASD (SRS-A score) and attachment (ASQ and ECR-R scores). To examine the relationship between SRS-A and attachment, Spearman correlation coefficients are computed. Sample size for Spearman correlation was determined using power analysis in G\*Power version 3.1.9.7 (Faul et al., 2007), using an alpha of 0.05, a power of 0.80, and an effect size of .5 for a two-tailed test. Because Spearman's rank correlation coefficient is computationally identical, power analysis was conducted using software for estimating power of a Pearson's correlation. Based on the aforementioned assumptions, the required sample size was determined to be 56. To prevent the hypotheses from being underpowered, we included a total of 60 participants for each hypothesis.

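### Section 4.4: the stated power-calculation inputs give a required sample size of 29, not 56, and nothing in the plan shows where 56 came from

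*Combined protocol and SAP*

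**What the plan says.** Section 4.4 names G\*Power 3.1.9.7 and gives all the inputs: "using an alpha of 0.05, a power of 0.80, and an effect size of .5 for a two-tailed test". The planned test is a Spearman correlation between SRS-A and the attachment scores. Because the authors regard the Spearman coefficient as computationally the same as Pearson's, "power analysis was conducted using software for estimating power of a" Pearson correlation. From these assumptions alone, "the required sample size was determined to be 56".

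One margin is then added: "To prevent the hypotheses from being underpowered, we included a total of 60 participants for each hypothesis". The total is repeated in the Summary and in Section 4.1 ("The study requires 60 participants"), with no further justification.

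Two other places bear on the figure. Section 8.1.1 describes four ASQ style scores and two ECR-R subscale scores. Section 10.1 sets the significance level without adjustment: "For the analyses p-value of < .05 was considered statistically significant".

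**The concern.** A correlation of .5 is large, and with conventional alpha and power it should need about 30 participants. The reported 56 is nearly twice that (56/29 = 1.93), which is too wide a gap for rounding or a difference between algorithms.

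If the figure does not follow from the inputs, then the number, an input, the routine or an unreported adjustment is misdescribed. A reader then cannot tell which effect the study was designed to detect. This affects how a null result is read. As written, 56 is the minimum for 80% power at .5, and 60 leaves four to spare. If the inputs are right and only the number is wrong, the study is sensitive to considerably smaller correlations than Section 4.4 implies.

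**Working it through.** **Inputs (all from Section 4.4).** Correlation under the alternative .5; two-tailed alpha .05; power .80; Pearson routine. Stated result: 56.

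**1. Attempt to reproduce 56.**

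- *Exact Pearson test.* I used the exact density of r under bivariate normality, with the critical value r_c = t/√(n − 2 + t²), where t is the 97.5% point of the t distribution on n − 2 degrees of freedom. Power for .5 is .7992 at n = 28, .8139 at n = 29, .9807 at n = 56 and .9866 at n = 60. The smallest n with power of at least .80 is **29**.
- *Fisher z.* n = 3 + [(1.960 + 0.842)/atanh(.5)]² = 3 + (2.8016/0.5493)² = **29.01**, or 30 if rounded up.

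The stated 56 is not reproduced.

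**2. Does the Spearman test explain it?** Section 4.4 says a Pearson routine was used, so no allowance should be present. With one:

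- Variance factor 1.06: 3 + 1.06 × 26.01 = 30.57, so 31.
- Variance factor 1 + r²/2 = 1.125: 3 + 1.125 × 26.01 = 32.26, so 33.
- Simulation under bivariate normality, 100,000 runs per cell. If .5 is the underlying Pearson correlation, power is .783 at n = 31 and .801 at n = 32. If .5 is the Spearman correlation itself (underlying Pearson .518), power is .789 at n = 29 and .806 at n = 30.

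The Spearman requirement is therefore 30-32 by simulation and 31-33 by approximation.

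**3. Does a margin or a correction explain it?**

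- *Dropout.* None is stated. Going from 29 to 56 needs 1 − 29/56 = 48%.
- *Multiplicity.* None is stated, and Section 10.1 tests at .05. Taking the SRS-A total (an assumption) against four ASQ and two ECR-R scores gives six tests; alpha .05/6 requires 43.

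**4. Does a changed input explain it?** Exact Pearson, all else as stated:

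| Change | Required n |
|---|---|
| One-tailed | 23 |
| Power .90 / .95 / .98 / .99 | 37 / 46 / 56 / 64 |
| Alpha .01 | 42 |
| Alpha .05/8 | 45 |
| Alpha .05/30 | 56 |
| Correlation .36 / .364 / .37 | 58 / 56 / 55 |
| One-tailed with power .99 | 55 |
| Alpha .05/6 with power .90 | 54 |
| Alpha .05/8 with power .90 | 56 |

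Other routines also come close. A single regression coefficient at f² = .15 needs 55, and comparing two independent correlations by Fisher z gives 55.02, so 56 per group. Several changes of one or two settings therefore reach or approach 56. The plan states none of them, and they contradict one another, so the cause cannot be inferred.

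**5. What 56 and 60 actually provide (per unadjusted test, complete records).**

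| | Pearson, exact | Spearman, simulated |
|---|---|---|
| Power for .5 at n = 56 | .981 | .967-.977 |
| Power for .5 at n = 60 | .987 | .975-.983 |
| Correlation with 80% power at n = 60 | .352 | about .36 |

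The Spearman ranges span the two readings of .5 in step 2. Coarse scores change little: with one variable rounded to 25 levels (SD 4 points; both assumed), Spearman power at n = 60 is .973-.982.

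**The case against.** The strongest reply is that nothing is harmed. The study is cross-sectional, with three short online questionnaires and no intervention, and its objective is exploratory. The error is conservative: if the stated inputs are right, no correlation test loses power at .5. Even at alpha .05/6, power for .5 with 60 participants is .937 (Pearson). On this view it is a reporting slip. That is a fair account of the consequences, and it limits the weight of the point, but it does not rescue the figure. It also assumes that the inputs are right and the number wrong. If the effect size, power or routine was misreported instead, the study was sized for something other than what it says.

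A second reply is that a single changed setting, such as power .98, gives exactly 56, so the sponsor may simply have entered something different. That is possible, but several settings fit equally well and Section 4.4 states power .80.

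A third reply is that the Spearman figures go beyond what Section 4.4 claims, since it states a Pearson routine. This is right as far as the error goes: 29 against 56 is enough to establish it. The Spearman figures show only that the planned test does not close the gap.

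Finally, the check covers the correlations alone. Sections 2 and 10.1 also plan a description of attachment styles and multiple regression, for which no precision or power is given. Nothing here shows that 60 is adequate for those.

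**Conclusion.** The concern holds. From the stated inputs and routine the required sample size is 29 (exact) or 30 (Fisher z rounded up), and about 30-33 with an allowance for the Spearman test, against 56 as reported. The inputs are all in Section 4.4, and the only assumption needed is bivariate normality, the usual model for a Pearson power calculation.

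The discrepancy is a factor of about 1.9 in the conservative direction. It misstates the relation between sample size, effect and power but does not undermine the planned correlation tests at .5. The source of 56 is unknown and cannot be settled from the documents. This should be fixed. It is not a reason to change enrolment.

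**What to change.** Leave the planned 60 as it is, re-run the calculation, and amend Section 4.4 in one of two ways.

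- **If other settings produced 56**, report the routine, effect size, alpha, power, sidedness and any adjustment exactly as they were entered. Do not solve backwards for an effect size that fits 56.
- **If the stated inputs are right**, replace the sentence giving 56. Suggested text: *For a correlation of .5, two-tailed alpha .05 and power .80, the required sample size is 29 for a Pearson test (exact bivariate-normal model) and about 30-32 for a Spearman test (simulation under bivariate normality). We include 60 participants. Under the same assumption, 60 complete records give about 97-98% power per unadjusted Spearman test for .5, and 80% power for a correlation of about .35 (Pearson) to .36 (Spearman).* If the sponsor prefers to report only the routine it ran, the Pearson figures are sufficient: 29 required, .987 power at 60, and 80% power for .352.

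The cost is one repeated power calculation and a reworded paragraph. Enrolment, procedures and analysis do not change.
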